8.4 METHODS FOR ASSESSING, RECORDING, AND ANALYZING SAFETY

The recording and documenting of adverse events (ocular and non-ocular) begin when the subjects are exposed to the test article or study treatment. Adverse events reported before the use of test article or start of study treatment should be recorded as medical history. Untoward medical events reported after the subject’s exit from the study will be recorded as adverse events at the discretion of the Investigator.

All adverse events observed by the Investigator; reported by the subject spontaneously; or in response to direct questioning; will be recorded in the source document. Such documentation will include a description of the adverse event, time of onset, duration of event, treatment regimen instituted, any referral to another health care provider (if needed), any new concomitant medications, outcome, ocular damage (if any), and likely etiology. Best Corrected Visual Acuity (BCVA) should be recorded prior to the report of an adverse event (as part of the baseline evaluation), upon report of the subject’s report of the adverse event, and after the adverse event has resolved. All adverse events will be followed in accordance with licensing requirements.

All adverse events will be documented in the appropriate section of the subject’s Case Report Form (CRF).

In conjunction with the medical monitor, the Investigator will evaluate adverse events to ensure the events are categorized correctly. Elements of categorization will include:

Seriousness (see definition in Section 8.3)

Expectedness – i.e. if the event was unexpected or unanticipated in that it was not previously identified in nature, severity, or degree of incidence (see definition in Section 8.3)

Causality or Relatedness – i.e. the relationship between the test article and the adverse event (not related; doubtful; possible; probable; very likely - see definition in Section 8.3)

Adverse Event Intensity or Classification – Adverse event intensity is used to assess the degree of intensity of the adverse event (mild, moderate, severe for all events). In addition adverse event Classification is used to assess the severity of ocular adverse events (AE not requiring treatment, non-significant or significant see definition in Section 7.4).

Outcome – Fatal, not resolved, resolved, resolved with sequelae, resolving and unknown.

Actions Taken – None, temporarily discontinued, permanently discontinued, other action taken

Upon finding an adverse event, the Principal Investigator will document the condition on the follow-up visit worksheet source document and in the CRF's using photos or drawings (where appropriate) that detail size, location, and depth. He will also complete the Adverse Event Classification (AEC) Discovery form / eCRF. In addition, if an infiltrate(s) is present, he will complete the Corneal Infiltrate Assessment Form / eCRF. Where necessary, a culture of the corneal lesion will be collected to determine if the infection is microbial in nature. If cultures are collected, a source document note should be completed specifying the date of culture collection and laboratory utilized. An eCRF documenting this should be completed in a comment or unscheduled visit.

Complete description of all adverse events must be available in the source documents. All Adverse Events including local and systemic reactions not meeting the criteria for "serious adverse events" should be captured on the appropriate case report form or electronic data system. Information to be recorded, based on above assessment criteria, includes date site notified, event description, date and time of onset, investigator assessment of severity, relationship to Study Agent(s)/Intervention(s), and time of resolution/stabilization of the event. All adverse events occurring while on study must be documented appropriately regardless of relationship. Define a timeframe for CRF completion and entry of the adverse event information into the database, as applicable.

Any medical condition that is present at the time that the subject is screened should be considered as baseline and not recorded as an AE. However, if the condition deteriorates at any time during the study it should be recorded and reported as an AE.

Changes in the severity of an AE should be documented to allow an assessment of the duration of the event at each level of intensity to be performed. Adverse events characterized as intermittent require documentation of the onset and duration of each episode. Changes in the assessment of relationship to the Study Agent(s)/Interventions should also be clearly documented.

The investigator will notify the Sponsor of an adverse event by e-mail, facsimile, or telephone as soon as possible and no later than 24 hours from discovery for a serious / significant adverse event, and 2 days from discovery for a non-significant adverse event. In addition, a written report will be submitted by the Principal Investigator to the IRB/IEC according to their requirements (Section 1212.3). Such a report should comment whether or not the adverse event was considered to be related to the test article.

8.5 ADVERSE EVENTS FOLLOW-UP

It is the Investigator's responsibility to maintain documentation of each reported adverse event. All adverse events will be followed in accordance with applicable licensing requirements. Such documentation will include the following:

- Adverse Event (Diagnosis not symptom)
- Detailed drawings or photographs, when appropriate
- Date and time of onset
- Date and time of resolution
- Adverse event intensity and classification, as applicable
- Treatment regimen instituted, including concomitant medications prescribed, in accordance with applicable licensing requirements
- Any referral to another health care provider if needed
- Outcome, ocular damage (if any)
- Likely etiology.

- Best corrected visual acuity at the discovery of the event and upon conclusion of the event

In addition, if an infiltrate(s) is present, the Investigator will complete the Corneal Infiltrate Assessment Form / eCRF.

Photographs or video recordings may be collected at the Investigator's discretion for purposes of documenting adverse event findings.

Visual acuity (best corrected) should be recorded prior to the report of an adverse event (as part of the Baseline Evaluation), upon the subject's report of the adverse event, and after the adverse event has resolved.

Subjects who present with adverse events should be followed by the Investigator, within licensure, until all signs and symptoms have returned to pre-treatment status, stabilized, or been satisfactorily resolved. If further treatment (i.e. beyond licensure) is required, the patient will be referred to the appropriate health care provider. The Investigator should use his/her clinical judgment as to whether or not a subject (eye) reporting with an adverse event should continue in the study. If a subject is discontinued from the study, it will be the responsibility of the Investigator to record the reason for discontinuation. The investigator will also complete the Adverse Event Classification (AEC) Outcome form / eCRF. Any subjects with ongoing adverse events related to the test article as of the final study visit date should be followed to resolution of the adverse event or until referral to an appropriate health care provider, as recommended by the Investigator.

9.1 STATISTICAL METHODS TO BE EMPLOYED

All data summaries and statistical analyses will be performed using the SAS software Version 9.4 (SAS Institute, Cary, NC). Throughout the analysis of data, the results for each subject/eye will be used when available for summarization and statistical analysis. Unscheduled visits will be summarized separately and will be excluded from the statistical analysis.

Summary tables (Descriptive statistics and/or frequency tables) will be provided for all baseline variables, efficacy variables and safety variables as appropriate. Continuous variables will be summarized with descriptive statistics (n, mean, standard deviation (SD), median, minimum and maximum). Frequency count and percentage of subjects or eyes within each category will be provided for categorical data.

Summaries will be presented by study lens type and will be performed separately by completion status (Completed or Non Completed). All analyses will be conducted on all subjects who completed the study (see section 9.7).

Primary Endpoint:

Overall quality of vision scores will be analyzed using a linear mixed model. The model will include the experimental design factors: time point (baseline/follow-up) as fixed effects. Other baseline characteristics known of importance such as age, gender, and/or add power will be included as fixed covariates when appropriate. Site will be included as random covariates when appropriate. The covariance between residual errors from the same subject across time points will be selected based on the finite-sample corrected Akaike's Information Criterion (Keselman et al. 1998). Covariance structures considered may include: Homogenous compound symmetry (CS) and Unstructured covariance structure (UN). The structure that returns the lowest Akaike Information Criteria Corrected (AICC) will be selected as the structure that best fit the data.

Comparisons between the time points will be carried out using 95% confidence intervals constructed of least-square means (LSM) differences (follow-up minus baseline) from the linear mixed model. The non-inferiority of the

test lens relative to the control will be concluded if the lower confidence limit of LSM difference is above the non-inferiority margin -5. The superiority will be established if the lower confidence limit is above 0.

In all models, the Kenward and Roger method (Kenward and Roger, 1997) will be used for the calculation of the denominator of degrees of freedom.

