1.8 PROTOCOL SYNOPSIS

| |
|---|
| Protocol Number and Title: CR-5903 Evaluation of a Novel Toric Multifocal Contact Lens in Hyperopic Presbyopes |
| Sponsor: JJVC, [name] |
| Investigational Products: Investigational Toric Multifocal Contact Lens for Presbyopia |
| Ancillary Supplies: ETDRS Light Box, Near Guillon-Poling Charts, Near Lamps, Guillon-Poling Chart Holder, Pupillometer, Rewetting drops, saline solution for final lens storage, and lens cases. |
| Randomization and Dispensing: Single Arm,(Non- Randomized) Dispensing trial |
| Microbiology or Other Testing Laboratory: Not Applicable |
| Phase or Type of Study: Feasibility |

Primary Objective: To evaluate the subjective feedback of a multifocal contact lens in a population of presbyopes with hyperopia.

Secondary Objectives:

- 1 – Evaluate the fit of the toric multifocal lens.
- 2 – Evaluate the ocular physiological response of the toric multifocal lens.

Study Design: This is a single-masked, single-arm, dispensing feasibility study. There will be three study visits. Visit 1 will include baseline measurements and screening to ensure eligibility. Eligible subjects will be fit in study lenses and dispensed for 6-8 days. At Visit 2 additional measurements will be performed and it will be determined if lens optimization is required and lenses dispensed for an additional 6-8 days. At Visit 3 the primary endpoint data used for analysis will be collected. The lenses will be worn as a daily disposable.

Sample Size: A total of approximately 60 eligible subjects will be enrolled into the study with 48 subjects targeted to complete. An attempt will be made to evenly distribute the subjects across the following ADD groups and ATR & WTR.

Distribution of the 48 Completed Hyperopes will be 24 ATR and 24 WTR

| +0.75 to +1.50 ADD | | +1.75 to +2.50 ADD | |
|-----------------------|-----|--------------------|-----|
| ATR | WTR | ATR | WTR |
| ≈12 | ≈12 | ≈12 | ≈12 |

Screening: Healthy male and female volunteers (from 40 to 70 years of age) with a need for presbyopic correction in both eyes will be screened as per criteria outlined below.

Qualification, Dispensing and Follow-Up Procedures:

Screening: Subjects will complete informed consent. Demographics and medical history will be reviewed and baseline measurements completed. Subjects must meet all of the study inclusion criteria to continue in the study.

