4.1 PRIMARY AND SECONDARY ENDPOINTS

The primary endpoint is overall quality of vision assessed using the Contact Lens User Evaluation questionnaire (CLUE™). CLUE is a validated Patient Reported Outcome (PRO) questionnaire developed to measure general and throughout the day comfort/vision, as well as symptoms of discomfort/poor vision, lens handling and packaging. Derived CLUE scores using Item Response Theory (IRT) follow a normal distribution with a population average score of 60 (SD 20), where higher scores indicate a more favorable/positive response. A 5 point increase in an average CLUE score translates into 10% shift in the distribution of scores for population of soft contact lens wearers.

The following one (1) primary hypothesis will be tested throughout this investigation. The primary hypothesis must be met to satisfy the objective of the study.

Primary Study Hypothesis

| | |
|---|--|
| 1 | After 12 to 16 days of wear, the CLUE vision score of the test lens will be non-inferior to subjects' habitual lens using a margin of -5 points. |
|---|--|

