4.2 INCLUSION CRITERIA

Potential subjects must satisfy all of the following criteria to be enrolled in the study:

1. The subject must read, understand, and sign the STATEMENT OF INFORMED CONSENT and receive a fully executed copy of the form.
2. The subject must appear able and willing to adhere to the instructions set forth in this clinical protocol.
3. Healthy adult males or females that are at least 40 years of age and no more than 70 years of age.
4. The subject must either be wearing a presbyopic contact lens correction (e.g., reading spectacles over contact lenses, multifocal or monovision contact lenses, etc.) or if not respond positively to at least one symptom on the "Presbyopic Symptoms Questionnaire". (Appendix B)
5. The subject is a current soft spherical or toric contact lens wearer (defined as a minimum of 6 hours of wear per day at least two days of the week for a minimum of 1 month prior to the study).
6. The subject's refractive spherical component must be between +1.25 D to +3.75D in each eye.
7. The subject's refractive cylinder must be -1.00D to -1.50D in each eye.
8. The subject's refractive cylinder axis must be $90^{\circ} \pm 30^{\circ}$ or $180^{\circ} \pm 30^{\circ}$ in each eye.
9. The subject's ADD power must be in the range of +0.75 D to +2.50 D in each eye.
10. The subject must have best corrected distance visual acuity of 20/20⁻³ or better in each eye.
11. The subject must have a wearable pair of spectacles if required for their distance vision.

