9.2 NUMBER OF SUBJECTS BY SITE AND JUSTIFICATION FOR SAMPLE SIZE

Approximately 60 eligible subjects will be enrolled and approximately 48 subjects are targeted to complete the study. Data from historical study CR 5758 and CR 5765 were used as the bench mark for sample size calculation because it tested the same population with the same study design and test article.

Using the POWER procedure in SAS 9.4, below is the summary of sample size required based on the different assumptions of the true difference. Each study hypothesis is tested with at least 90% of statistical power and 2-sided type I error of 0.05.

Several scenarios were listed in the table below to allow variations in the upcoming clinical trial:

| Difference (FU-Baseline) | Standard Deviation | # of subjects needed | Power |
|--------------------------|--------------------|----------------------|-------|
| 2 | 19 | 65 | 0.9 |
| 3 | 19 | 50 | 0.9 |
| 4 | 19 | 40 | 0.9 |

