9.5 PROCEDURE FOR ACCOUNTING FOR MISSING, UNUSED, AND SPURIOUS DATA

Missing or spurious values will not be imputed. The count of missing values will be included in the summary tables and listings. If the percent of dropout is higher than 15% a sensitivity analysis will be conducted on all subjects who successfully tried at least one study lens.

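### Does it matter that the primary model's covariates cannot move the estimate and that no result is planned by ADD and axis group?

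*Combined protocol and SAP*

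**What the plan says.** Section 9.1 fits a linear mixed model to the CLUE vision scores of subjects who completed the study. On fixed effects: "The model will include the experimental design factors: time point (baseline/follow-up) as fixed effects". On covariates: "Other baseline characteristics known of importance such as age, gender, and/or add power will be included as fixed covariates when appropriate". Site may enter as a random term, and no interaction with time is named. Non-inferiority is judged by the lower 95% limit of follow-up minus baseline against -5.

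On enrolment, section 1.8 says: "An attempt will be made to evenly distribute the subjects across the following ADD groups and ATR & WTR". Sections 1.8 and 2.6 show about 12 completers in each of four cells: ADD +0.75 to +1.50 or +1.75 to +2.50, crossed with against-the-rule (ATR) or with-the-rule (WTR). Criterion 8 in section 4.2 sets the range for the axis ("refractive cylinder axis must be") separately for each eye.

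On breakdowns of results, section 9.1 says: "Summaries will be presented by study lens type and will be performed separately by completion status (Completed or Non Completed"). On losses, section 9.2 says: "Approximately 60 eligible subjects will be enrolled and approximately 48 subjects are targeted to complete the study". Section 9.5 rules out imputation and adds: "If the percent of dropout is higher than 15% a sensitivity analysis will be conducted on all subjects", meaning those who successfully tried at least one study lens.

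**The concern.** Three things catch the eye.

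- **Covariates.** The covariate sentence reads like an adjustment of the primary comparison, but with complete pairs it adjusts nothing. Its wording also leaves the list open, which normally raises the worry that a model could be picked after seeing the data.
- **Enrolment cells.** The trial recruits deliberately across four cells, but section 9 never mentions ATR/WTR. Its only breakdowns are lens type, of which there is one, and completion status. An acceptable overall mean could hide a group that does badly.
- **Mixed eyes.** A subject may have one ATR and one WTR eye, while the CLUE score belongs to the subject. Without a rule, the 24/24 target can be counted in more than one way.

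At stake would be an estimate that depends on an open modelling choice, or a design feature that never reaches the report.

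**Working it through.** **Inputs.** Score SD 20 (section 4.1). SD 19, differences 2, 3 and 4, and required numbers 65, 50 and 40 (section 9.2). Margin -5 and the 95% interval (sections 4.1 and 9.1). 60 enrolled and 48 completing (section 9.2). SD 19 is taken as the SD of the paired change.

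**The plan's own figures.** A paired t-test with shift = difference + 5 and SD 19 gives 65, 50 and 40 at one-sided 0.05, an exact match that supports this reading of SD 19. The 95% interval rule (one-sided 0.025) would need 80, 62 and 49. That mismatch is a separate matter and does not bear on this point.

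**Why the covariates cancel.** Write subject i's scores as

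- baseline: y1 = m + x·b + s + e1
- follow-up: y2 = m + D + x·b + s + e2

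where x holds age, gender and ADD, and s is the site effect. Then y2 - y1 = D + (e2 - e1), so x and s drop out. The estimate is the mean change, with SE = SD(change)/√n.

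One simulated set of 48 complete pairs was fitted by REML under compound symmetry and unstructured covariance, with five covariate sets: none; age; age, gender and ADD; those plus ATR/WTR; and age, gender and ADD with random site. All ten fits gave 0.84585 with SE 2.64805, equal to the plain paired mean and SD/√n. An ATR/WTR main effect therefore cancels too.

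**Planned precision.** SE = 19/√48 = 2.742. Half-width = 2.012 × 2.742 = 5.52. Power at a true difference of 3 is 0.815.

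**What results by group could show** (SD 19 assumed within groups):

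| Group | n | 95% half-width | Power at difference 2 / 3 / 4 |
|---|---|---|---|
| One ATR or WTR half | 24 | 2.069 × 19/√24 = 8.02 | 0.41 / 0.51 / 0.60 |
| One cell | 12 | 2.201 × 19/√12 = 12.07 | 0.21 / 0.27 / 0.32 |

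The difference in change between two halves of 24 has half-width 2.013 × 19 × √(2/24) = 11.04.

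**Would cell-by-time terms help the primary analysis?** With 12 per cell and observed weights, power at difference 3 is 0.814 if cells do not differ, and 0.820 or 0.841 if the between-cell SD of change is 2.5 or 5 (both assumed), against 0.815 as planned. If cell counts are left to chance, coverage in the two heterogeneous cases is 94.8% and 94.2%.

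**Where covariate choice can act.** It can act where one score is missing. One case is a completer lacking a CLUE score: section 9.7 does not require both scores and section 9.5 does not impute. The other is subjects with only a baseline score in the section 9.5 sensitivity analysis, if that reuses the section 9.1 model. The planned loss is (60 - 48)/60 = 20%, above the 15% trigger if all of it counts as dropout.

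Trials with 60 baseline and 48 follow-up scores were simulated with score SD 20. SD 19 for the change implies a within-subject correlation of 1 - 361/(2 × 400) = 0.549. Covariates were assumed to explain 5% to 20% of score variance. The spread of the contrast over all eight subsets of age, gender and ADD was:

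- random dropout: median 0.18 to 0.37 points, 95th percentile 0.47 to 0.79
- high-ADD subjects dropping out three times as often (assumed): 95th percentile 0.62 to 1.04

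Against the 5-point margin, the medians are 0.18/5 = 4% to 0.37/5 = 7%, and the worst 95th percentile is 1.04/5 = 21%. Sixty baselines is an upper limit, since subjects who leave at Visit 1 for poor fit or vision may not count as having successfully tried a lens.

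**The case for a change.** The case for acting is that the fixes are cheap and the gaps are real. Axis, ADD and the dominant eye are recorded at Visit 1. A trial that sets out cell targets in two sections might be expected to show change in those cells. In the simulated data above, where cell effects were deliberately made unequal, an overall change of +0.85 covered observed cell means from +9.2 to -10.3, and the covariates revealed none of it. The sensitivity analysis is likely to be triggered, and it is the main place where an open covariate list can move an estimate.

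The factual part of this stands: section 9 does not mention ATR/WTR, the list is open, and the visible text has no rule for mixed eyes (the fitting guide in Appendix E is not shown).

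The inference to a needed change does not stand:

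- Covariates that cannot move the primary estimate cannot be chosen to favour a result.
- Spreading recruitment over a product range of six axes and three ADD powers (section 2.1) is a reasonable aim in itself and does not promise subgroup results.
- The cell target is an attempt at approximate numbers. No planned analysis uses the cells, so classification of mixed eyes affects only an enrolment count.
- Section 9.1 already promises summary tables of baseline variables, so the achieved ADD and axis mix can be reported.

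**Conclusion.** No change follows. For completers with both CLUE scores, the section 9.1 contrast is the paired mean change with a valid interval, whatever main-effect covariates are added. Cell-by-time terms offer no dependable gain: power moves from 0.815 to between 0.814 and 0.841 under assumed heterogeneity, and coverage can fall slightly below 95%.

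This is a feasibility study with one hypothesis, about the overall score. Results by group would carry intervals of ±8.0 to ±12.1 points and could only be descriptive. An analyst who wants them can produce simple mean changes by ADD band and by ATR/WTR, and can state in the report how mixed-axis subjects were counted. Fixing the covariate list before database lock is sensible practice, but the choice is worth a few tenths of a point at the median, and about one point at the worst 95th percentile, in a secondary analysis.

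This rests on SD 19 being the SD of the paired change and holding within groups, on few completers lacking a CLUE score, and on the assumed dropout and covariate strength in the sensitivity simulation. The cancellation itself needs only complete pairs and covariates that do not interact with time.
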